## 10.13 Data Management

A unique personal identification number will be used to identify study subjects on all data forms and on all CRFs and electronic SENSE measurement data collected by the Sponsor. This will ensure proper compliance with HIPAA regulations. Instructions for completing the data forms will be addressed in detail in the CRF instruction guide. Data is expected to be entered onto the CRFs within 10 calendar days after SENSE monitoring is completed. The SENSE measurement data will be exported onto a USB drive or other electronic medium by the Sponsor at the conclusion of the SENSE monitoring for each subject. A file will be maintained of all relevant study documentation for a period of at least two years after the investigation is completed or discontinued and the FDA (Food and Drug Administration) has been notified by the Sponsor.

## 11.0 Ethical and Regulatory Considerations

The study is being conducted in accordance with the following GCP regulations:

- 21 CFR § 812 Investigational Device Exemption regulations;
- 21 CFR § 50 Protection of Human Subjects (informed consent) regulations;
- 21 CFR § 56 Institutional Review Boards; and,
- 21 CFR § 54 Financial Disclosure

All sites are located in the U.S., and no international sites are included in the study. Clinical monitoring is being conducted throughout the study in conformance with FDA's *Guideline for the Monitoring of Clinical Investigations* and *Guidance for Industry Oversight of Clinical Investigations – Risk-Based Approach to Monitoring*.

The clinical study will be registered on [www.clinicaltrials.gov](http://www.clinicaltrials.gov) (ID Number to be assigned).

### 11.1 Informed Consent

In accordance with the provision of 21 CFR Part 50 and 21 CFR Part 50.25 (Elements of Informed Consent; Appendix B), each subject will provide written informed consent for participation in this study prior to the use of the investigational device.

The study will be explained to the prospective subject (or to the next of kin or legal representative for obtunded patients) by the investigator or his designee. The nature of the experimental product will be explained, including any possible adverse reactions. It will also be explained that the subject is free to terminate participation in the study for any reason. One copy of the signed consent form will be retained in the medical record, and one copy will be given to the subject.

## **11.2 Institutional Review Board**

This protocol and the ICF will be approved initially and reviewed annually by an Institutional Review Board (IRB) constituted according to FDA regulations. Progress reports will be submitted at the completion of the study or at least once yearly, whichever comes first, to the IRB. Serious adverse events will be reported to the IRB and the FDA in accordance with applicable FDA regulations for serious adverse events.

## **11.3 Complications and Adverse Events**

Device related adverse events should be recorded on the CRFs. For all adverse events and complications, a description of the event, date first observed, any action taken, relationship to device and ultimate outcome will be recorded. The ascertainment of relationship to the device will be performed by the independent safety monitor.

Any possible seizure related events that are observed by the investigator, or recorded in the chart notes or observed by nursing or medical personnel or reported by the subject, should be recorded and evaluated as a potential adverse event.

All device related adverse events should be recorded on the adverse event forms on the CRFs. Adverse device effects or events that are determined by the independent safety monitor to be neurologically threatening or result in a worsening of neurological status should be considered to be reportable according to the requirements of Sections 11.3.1, 11.3.2, and 11.3.3 below.

Observations that, after independent safety monitor review, are determined to be part of the normal clinical course that occur after an intracranial hemorrhage and unrelated to the SENSE device are not considered to be reportable events.

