## **6.0 Endpoints**

The primary endpoint for this early feasibility study is the correlation of the SENSE signal with CT changes over time.

Secondary endpoints will include the ability to process collected data in a manner that allows application and use of the SENSE device in a clinical environment and a preliminary estimate of the safety of the device when used in a clinical setting. Serious, unexpected adverse events will be recorded. Epileptic seizures will be an adverse event of special interest and recorded regardless of serious or unexpected status.

Qualitative information regarding device tolerability and compatibility with ICU workflow will be obtained from study subjects and ICU staff.

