### **9.7 Safety Monitoring**

The presence or absence of device related adverse events or complications, including epileptic seizures, occurring during the 72-hour SENSE monitoring period or emerging after the SENSE headset was removed (up to 7 days of hospital stay) will be documented.

A neurologist at the University of Cincinnati, who is not affiliated with the study or Sense Diagnostics, will serve as the independent safety monitor for this first-in-man study. The independent safety monitor will review adverse events and seizures for all subjects enrolled to detect any device related adverse events that may occur while the SENSE device is being worn or that emerged after exposure to the SENSE device. All adverse events, including seizures, determined to be device related will be recorded on the CRFs. The independent safety monitor will evaluate the incidence of seizures compared to the study stopping rules in Section 10.2 below to determine if early study termination is warranted.

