#### **11.3.2 Non-serious or Anticipated Adverse Events**

Non-serious or anticipated adverse events and complications should be documented on the CRFs and tabulated for reporting but need not be submitted as individual reports by the investigator to the sponsor or IRB. Should the IRB have different reporting requirements, the requirements of the IRB will be followed.

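### The adverse event recording and tabulation rules conflict: some depend on one monitor's judgement of device relatedness and others do not, so the safety tables can be filtered by attribution

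*Combined protocol and SAP*

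**What the plan says.** Some rules depend on relatedness to the device:

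- Section 9.7: "All adverse events, including seizures, determined to be device related will be recorded on the CRFs". This follows the description of the monitor's review.
- Section 11.3 says it twice: "Device related adverse events should be recorded on the CRFs" and "All device related adverse events should be recorded on the adverse event forms on the CRFs".
- Section 9.5.2 directs the day-7 review of inpatient records at device-related events and epileptic seizures.
- Section 10.6 tabulates what is captured on a forced-choice CRF, then adds other events if they are device related.

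The decision belongs to one person. Section 11.3: "The ascertainment of relationship to the device will be performed by the independent safety monitor". Section 9.7 says that a neurologist not affiliated with the study or the sponsor "will serve as the independent safety monitor for this first-in-man study".

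Other rules have no relatedness condition:

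- Section 11.3, directly after its first device-related sentence: "For all adverse events and complications, a description of the event, date first observed, any action taken, relationship to device" and outcome are to be recorded.
- Section 11.3.2: "Non-serious or anticipated adverse events and complications should be documented on the CRFs and tabulated for reporting".
- Section 6.0: "Serious, unexpected adverse events will be recorded". This is limited by seriousness and expectedness, not by cause.
- The 6-week call in sections 9.2 and 9.5.2 asks about adverse events generally.

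**The concern.** Section 5.0 makes safety one of two primary objectives. Section 2.2 says there is no earlier human experience, and section 7.0 describes up to 10 subjects at one site with no control group. Section 4.0 expects ICH-related events such as re-bleeding, seizures, headache and cognitive impairment to be common. Against that background, case-by-case attribution is weakest for a device harm that looks like the disease.

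If attribution decides what is recorded or tabulated, the judgement cannot be re-examined from the tables. It also leaves no unfiltered adverse event rate for planning the pivotal study, which sections 5.0 and 10.1 name as a purpose of this one. Staff completing the CRFs could follow either set of rules and believe they were complying.

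**Working it through.** The plan gives no figure on this point, so the check is a comparison of its rules.

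| Section | What it governs | Relatedness condition? |
|---|---|---|
| 9.7 | Entry on CRFs | Yes; seizures are named in the same sentence |
| 11.3, two sentences | Entry on CRFs and adverse event forms | Yes |
| 9.5.2 | Day-7 record review | Yes, except epileptic seizures |
| 10.6 | Tabulation of events outside the forced-choice form | Yes |
| 10.6 | Tabulation of the forced-choice form | None stated |
| 11.3, all-events sentence | Details and relationship recorded; place not stated | No |
| 11.3.2 | CRF entry and tabulation of non-serious or anticipated events | No |
| 6.0 | Recording of serious, unexpected events | No |
| 9.2, 9.5.2 | 6-week call | No |

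1. **Recording.** Take a non-serious or anticipated event that the monitor judges unrelated. Section 11.3.2 puts it on the CRF. Sections 9.7 and 11.3 name only device-related events for the CRF.
2. **Tabulation.** If that event is not an item on the forced-choice form, section 11.3.2 tabulates it and section 10.6 does not include it.
3. **Serious but expected events.** Section 6.0 covers events that are both serious and unexpected. A serious event of an expected kind that is judged unrelated falls outside section 6.0 and outside the device-related rules. It reaches the CRF only if 11.3.2 is read to include it as anticipated, or if the all-events sentence of 11.3 is taken to mean the CRF.
4. **Seizures.** Sections 6.0 and 10.6 record them whether or not they are serious or unexpected. Neither mentions relatedness, while section 9.7 includes seizures in its device-related sentence.
5. **Which rule governs.** No section says. Section 10.0 states that no detailed SAP will be written. Section 10.13 mentions a CRF instruction guide, which is not among the documents.

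**Illustration of size, with assumed inputs.** Let n = 10 (section 7.0). Let p be the true per-subject rate of an event outside the forced-choice form, and s the probability that the monitor calls it device related. Neither p nor s is in the documents. If the narrow rules are followed, P(no event tabulated) = (1 − p·s)^10.

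| p | s = 1 (same as no filter) | s = 0.5 | s = 0.25 |
|---|---|---|---|
| 0.20 | 0.80^10 = 0.11 | 0.90^10 = 0.35 | 0.95^10 = 0.60 |
| 0.30 | 0.70^10 = 0.03 | 0.85^10 = 0.20 | 0.925^10 = 0.46 |

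A table showing 0/10 has an exact one-sided 95% upper limit of 1 − 0.05^(1/10) = 25.9%. With the filter, that limit applies to p·s and not to p. At s = 0.5, for example, the limit for p would be 25.9% / 0.5 = 51.8%.

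**The case against.** The strongest reply is that the plan nowhere says an unrelated event is kept off the CRF. The all-events sentence of 11.3 already requires the relationship to the device as a recorded item, which is the core of the fix. Section 11.3.2 sends anticipated events to the CRF and the tables, and section 4.0 names re-bleeding as an expected ICH event. The monitor reviews adverse events for all subjects, and Appendix A schedules adverse event assessments without a relatedness condition. This stands as far as it goes: exclusion is an inference from 9.7, 10.6 and 11.3. It does not remove the conflict, because 10.6 is the safety analysis section and, outside the form, includes only device-related events.

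A reader might infer that re-bleeding or neurological worsening judged to be normal disease course never enters the database. The documents do not support that. A blinded neuro-radiologist measures haemorrhage volume (9.4). CTs done for deterioration before the 72-hour scan are collected and analysed (7.0, 9.2). NIHSS and GCS are taken at baseline, 12 and 72 hours (9.5.2), and reasons for withdrawal are tabulated (10.4). The possible gap is in the adverse event tables. Likewise, the sentence in 11.3 that makes normal-course events not reportable concerns reporting; it does not exclude them from the CRF.

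It is also tempting to measure the damage by comparing 0/10 (upper limit 25.9%) with 2/10 (upper limit 50.7%). The two events are hypothetical, and the comparison sets a device-related rate against an all-cause rate.

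Three further points stand. The forced-choice form's items are not shown, so the extent of filtering is unknown. The analysis is descriptive with no success criteria (10.0, 10.8). Section 6.0 lists safety as a secondary endpoint, although 5.0 makes it a primary objective.

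**Conclusion.** The contradiction holds, and the plan does not resolve it. Following 10.6 as written would give a safety summary that, outside the forced-choice form, has already passed through one monitor's attribution. Serious or neurological events judged to be normal ICH course could then be absent from the adverse event tables, though partly visible in the CT, NIHSS and GCS data.

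The size cannot be derived from the documents. The illustration shows only that the effect need not be small: with an assumed true rate of 30%, the chance of an empty table rises from 0.03 to 0.20 when half the events are judged related, and to 0.46 when a quarter are. It assumes that subjects are independent, that s is the same for all, and that the event is not on the forced-choice form. The headset effects listed in 9.5.3 are probably on that form, which is also an assumption.

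This should be corrected because safety is a primary objective and the correction is cheap. It is not evidence that harms are being kept out of the study data.

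**What to change.** Reconcile sections 6, 9.5.2, 9.7, 10.6, 11.3 and 11.3.2 to one rule:

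- **Record** on the CRF every serious and every neurological adverse event from headset placement to discharge or day 7, whichever is first, plus those reported at the 6-week call, regardless of relatedness.
- **Keep** the monitor's relatedness judgement as a data field on each event, not as a condition for entry.
- **Tabulate** all events first and device-related events second.

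The same amendment can tidy two loose ends. Section 11.3 refers to a section 11.3.3 that does not exist, and Appendix A marks only the serious adverse event assessment at 6 weeks while 9.2, 9.5.2 and 9.5.3 cover adverse events generally.

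The cost is amendment wording and some extra CRF entries for at most 10 subjects. No visit is added, because inpatient records are already reviewed over that window and the 6-week call is already planned. The all-event table will include disease-course events and will not by itself separate device effect from disease. It does keep the attribution open to inspection and leaves an unfiltered rate, for the events covered, to use in planning the pivotal study.

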### **11.3.1 Serious and Unanticipated Adverse Device Effects**

An unanticipated adverse device effect is defined as “any serious adverse effect on health or safety or any life-threatening problem or death caused by, or associated with, a device if that effect, problem, or death was not previously identified in nature, severity, or degree of incidence in the investigational plan, or any other unanticipated serious problem associated with a device that relates to the rights, safety or welfare of subjects.”

#### **11.3.1.1 Sponsor Responsibilities**

In accordance with 21 CFR Part 812.150(a)(1) and (b)(1), the sponsor shall promptly report the results of an evaluation of any serious and unanticipated adverse device effect to FDA, all reviewing IRB’s and participating investigators (if any) as soon as possible, but not later than 10 working days after the sponsor first receives notice of the effect. Thereafter, the sponsor shall submit such additional reports concerning the effect as the FDA requests. Complications and non-serious or anticipated adverse events should be

documented and tabulated but need not be submitted by the sponsor to the FDA as individual reports.

#### **11.3.1.2 Investigator Responsibilities**

Investigators should report all serious and unanticipated adverse events to the sponsor within 10 working days of first learning of the event. Those that are determined to be serious and unanticipated after independent safety monitor and sponsor review should also be reported to the IRB within 10 working days of first learning of the event. Should the IRB have more stringent time requirements, the reporting requirements of the IRB will be followed.

#### **11.3.2 Non-serious or Anticipated Adverse Events**

Non-serious or anticipated adverse events and complications should be documented on the CRFs and tabulated for reporting but need not be submitted as individual reports by the investigator to the sponsor or IRB. Should the IRB have different reporting requirements, the requirements of the IRB will be followed.

### **11.4 Monitoring**

A monitor will be designated by the sponsor to oversee the progress of the investigation. The monitor may be an employee of the sponsor or a consultant to the sponsor. The monitor will meet with the investigator and staff before the study, during the study, and at other appropriate times to ensure compliance with the FDA's Good Clinical Practice (GCP) requirements and with the protocol specifications. All records pertaining to the study will be made available to the monitor at each review.

Study initiation and training activities may be conducted in a variety of formats prior to the start of the study, including centralized investigator meetings, web conferences, self-study of training modules on selected topics, and on-site initiation visits.

The monitor will review study activities periodically during the study to identify any problems. Data will be verified for accuracy and thoroughness using the most appropriate source documents for all subjects. A monitoring report will be issued after each monitoring visit that summarizes current enrollment, activities reviewed during the monitoring visit, and any outstanding items or issues that require correction. The close out monitoring visit will take place at the completion of the study.

### **11.5 Source Documents / Case Report Forms**

Adequate records will be maintained for the study including subject medical and surgical records, signed informed consent forms (ICFs), and device use records. All original source documentation will remain at the investigative site. Study data that are stored at the investigator site in any electronic medical records system, including measurements

that are obtained electronically (e.g., radiology or laboratory reports), will be printed and retained in the study files.

All study data will be recorded onto CRFs (electronic or paper) designed for the study. If paper CRFs are used, copies of the CRFs will be retained with the investigator's study files; and the original forms will be filed with the sponsor. The sponsor will enter the data from the paper CRFs into a database designed for the study.

The display screen for the SENSE device is disabled and the investigator is masked from the SENSE measurements. Data from the SENSE measurement device will be exported and stored on a USB or other electronic medium for analysis by the Sponsor. The Sponsor will provide the investigator with any available printouts from the SENSE device at the conclusion of the study for inclusion in the investigator's study files.

### **11.6 Deviation from the Protocol**

The investigator will not deviate from the protocol without prior IRB and sponsor approval, unless such deviation is necessary to manage a medical emergency. The investigator will notify the IRB and the sponsor of any protocol deviation to protect the life or physical well-being of a subject in an emergency. Such notice shall be given as soon as possible, but in no event any later than 5 working days after the emergency occurred. All other revisions and/or amendments to the protocol that affect subject treatment, study outcome, or subject safety should be submitted in writing to the IRB and the sponsor for approval prior to implementation, if the changes or deviations to the protocol affect the scientific soundness of the study or the rights, safety, or welfare of human subjects. In this case, the change should not be implemented until IRB and sponsor approvals are obtained. The investigator should maintain a record of all protocol deviations showing the dates of, and the reason for, each protocol deviation.

Changes that affect the scientific soundness of the study or the rights, safety, or welfare of human subjects may also require FDA approval, in addition to sponsor and IRB approval, prior to implementation. The sponsor and investigator will obtain such approvals, if required.

**APPENDIX A: Study Flow Chart**

Time	Screening	Baseline	<del>Every 10 minutes for</del> 72 hour SENSE Monitorings	12 (±6) hours	72 (±12) hours	6 (±2) weeks
Assessments / Outcome Measures / Labs / Procedures	X	X		X	X	
Informed Consent	X					
History & Physical	X	X				
NIH Stroke Scale	X	X		X	X	
Glasgow Coma Scale	X	X		X	X	
CT scan	X	X		X	X	
Intermittent or Continuous SENSE Measurement		X	X	X	X	
Adverse event assessment	X	X		X	X	
Serious adverse event assessment	X	X		X	X	X
Phone call for safety monitoring						X

## **APPENDIX B: CFR 50.25 - ELEMENTS OF INFORMED CONSENT**

**BASIC ELEMENTS OF INFORMED CONSENT:** In seeking informed consent, the following information shall be provided to each subject.

1. A statement that the study involves research, an explanation of the purpose of the research and the expected duration of the subject's participation, a description of the procedures to be followed, and identification of any procedures which are experimental.
2. A description of any reasonably foreseeable risks or discomforts to the subject.
3. A description of any benefits to the subject or to others which may reasonably be expected from the research.
4. A disclosure of appropriate alternative procedures or courses of treatment, if any, that might be advantageous to the subject.
5. A statement describing the extent, if any, to which confidentiality of records identifying the subject will be maintained and that notes the possibility that the U.S. Food and Drug Administration may inspect records.
6. An explanation of whom to contact for answers to pertinent questions about the research and research subject's rights, and whom to contact in the event of a research-related injury.
7. A statement that participation is voluntary, that refusal to participate will involve no penalty or loss of benefits to which the subject is otherwise entitled, and that the subject may discontinue participation at any time without penalty or loss of benefits to which the subject is otherwise entitled.
